#### 502 *Sample Size*

503 With a change in blood pressure of 5mmHg, which has previously been shown to be clinically  
504 significant (12,13), a standard deviation of 17.6mmHg, a power of 80%, and an alpha of 0.05 there would  
505 need to be 312 patients enrolled. With allowance for 20% loss to follow-up, the study will seek to enroll  
506 390 patients total to have an 80% power with an alpha of 5%. With a standard deviation of 1.6 (8) and a  
507 sample size of 390 patients, we will be able to detect a 0.5 Morisky score difference between the groups  
508 with a power of 87%.

509

510 Summary of changes to analytic plan

511 More concrete analysis methods for evaluating baseline patient characteristics as well as a list of  
512 potentially unmatched covariates are now provided which was not included in the original plan. Missing  
513 12-week outcome data is also addressed in the final plan, specifically performing multiple imputation via  
514 the PROC MI function in SAS.

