267 unable to activate the smartphone application associated with the blood pressure monitor, they may  
268 submit their blood pressure readings by taking a time-stamped photo of the blood pressure monitor  
269 display. Blood pressure will be calculated as the average of two measurements that are taken five minutes  
270 apart, which is in accordance with previous literature (14). Once their blood pressure readings have been  
271 confirmed as being elevated, patients will undergo randomization in a 1:1 ratio to intervention or control  
272 using simple randomization through a random number generated at the time of study enrollment.

273

274 ***Informed Consent***

275 Informed consent will be attained from subjects prior to enrollment using an eConsent process.  
276 Patients will be told that a study is being conducted for evaluation of blood pressure, and focused on  
277 strategies to optimize treatment using technology. They will also be informed of how their personal  
278 information will be secured and that all analysis will be conducted on de-identified data. Because  
279 Medisafe is a free application and notification may lead to use of this technology in the control arm,  
280 patients will not be told about Medisafe before randomization. After randomization patients in the  
281 intervention arm will be provided with information and instructions to download Medisafe. During the  
282 informed consent process, there will be a contact form as well as a phone number and email available to  
283 patients for any questions or to withdraw from the study.

284

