387 correlations between repeated blood pressure readings for any individual subjects. If there are additional  
388 blood pressure readings from patients who took their blood pressure more often than required, the  
389 longitudinal models will be re-run to include these additional values.

390 In subgroup analyses, we will evaluate whether the impact of Medisafe differed for subjects who  
391 interacted with Medisafe frequently (defined as being in the upper median of use for the Medisafe  
392 application based on number of days logged in during the study period) as compared to subjects who  
393 interacted with Medisafe less frequently. We will perform this analysis by including categorical variables  
394 for high and low use in our outcome model, whereby control subjects are indicating by null values for

395 both indicators. We will also evaluate effect modification by hypertension knowledge (16) recorded at  
396 baseline.

397

398 ***Sample Size***

399 With a change in blood pressure of 5mmHg, which has previously been shown to be clinically  
400 significant (12,13), a standard deviation of 16.7mmHg, a power of 80%, and an alpha of 0.05 there would  
401 need to be 312 patients enrolled. With allowance for 20% loss to follow-up, the study will seek to enroll  
402 390 patients total to have an 80% power with an alpha of 5%. With a standard deviation of 1.6 (8) and a  
403 sample size of 390 patients, we will be able to detect a 0.5 Morisky score difference between the groups  
404 with a power of 87%.

405

406 ***Risks Associated with the Intervention***

407 Since the intervention under investigation is not aimed at altering a patient's treatment, but rather  
408 to promote adherence to treatments that they have already been prescribed, the risk will be minimal.  
409 There is a possible risk of patients receiving escalating anti-hypertensive medications from their treatment  
410 team due to non-adherence, and with the better adherence through Medisafe reminders there could be  
411 medication induced hypotension. During the informed consent process and on the blood pressure  
412 measurement guidance sheet there will be recommendations to reach out to their treatment team if they  
413 ever have a blood pressure > 180/120 mmHg or < 90/50 mmHg. The informed consent will also clearly  
414 state that no component of the study, including the home blood pressure cuff use and study personnel, is a  

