458 clinically significant (12,13), a standard deviation of 17.6mmHg, a power of 80%, and an alpha of 0.05  
459 there would need to be 312 patients enrolled. With allowance for 20% loss to follow-up, the study will  
460 seek to enroll 390 patients total to have an 80% power with an alpha of 5%. With a standard deviation of  
461 1.6 (8) and a sample size of 390 patients, we will be able to detect a 0.5 Morisky score difference between  
462 the groups with a power of 87%.

463

464 Final analytic plan

465 *Analytic Plan*

466 The Center for Healthcare Delivery Science (C4HDS) at Brigham Women's Hospital will  
467 conduct all analysis on de-identified data. Analyses will be performed by an intent-to-treat basis, where  
468 subjects will be analyzed in the groups they are assigned to during randomization.

469 We will begin by comparing the baseline patient characteristics in each of the arms using t-tests,  
470 chi-square tests or their non-parametric analogues, as appropriate. We will evaluate for rates of missing  
471 data between the two study arms to ensure that it is non-differential.

472 We will use linear regression to assess the impact of Medisafe on the study's 2 primary outcomes  
473 (change in blood pressure and self-reported adherence) between the two study groups. Our null  
474 hypothesis will be that there is no difference in the change in blood pressure between the two groups after  
475 12 weeks.

476 Our primary models will adjust for unbalanced covariates between the two groups (i.e. age,  
477 gender, ethnicity, BMI, comorbidities, number of antihypertensive medications, total number of  
478 medications, education, exercise level, cell phone use) should any exist using a p-value threshold of 0.05  
479 and will impute missing outcome data where 12 week outcome data is unavailable. Imputation will be  
480 performed using the PROC MI command in SAS and will include the covariates defined above as well as  
481 intermediate outcomes (i.e. blood pressure at weeks 4 and 8). Multiple imputation with 5 imputations  
482 will be used and the imputed values will be inspected to ensure in-range values. After imputation,  
483 analyses will be conducted on the imputed data set and the results will be combined using the standard  
484 rules from Rubin et al. In sensitivity analyses, we will analyze only those subjects for whom we have  
485 complete outcome data (i.e. a complete case analysis).

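### 312 evaluable patients do not give 80% power for 5 mmHg at either stated SD: two-sided power is about 71–75%, and the final protocol and final analytic plan disagree on the SD

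*Supplement*

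**What the plan says.** Both final documents carry the same sample-size paragraph apart from one number.

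- **Final analytic plan, Sample Size:** the target is introduced by "With a change in blood pressure of 5mmHg", and the variability and error rates by "a standard deviation of 17.6mmHg, a power of 80%, and an alpha of 0.05 there would". The result follows: "need to be 312 patients enrolled. With allowance for 20% loss to follow-up, the study will seek to enroll" 390.
- **Final protocol, Sample Size:** the effect, power, alpha, 312 and 390 are the same, but the assumption is "a standard deviation of 16.7mmHg, a power of 80%, and an alpha of 0.05 there would".

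Both then claim "390 patients total to have an 80% power with an alpha of 5" percent. Allocation is equal: "patients will undergo randomization in a 1:1 ratio to intervention or control" (final protocol, Subject Recruitment and Randomization). Neither sample-size section says whether the test is one- or two-sided. Neither says whether the SD is that of the change or of a single reading. The Analytic Plan section of both gives the null without a direction: "hypothesis will be that there is no difference in the change in blood pressure between the two groups after" 12 weeks. Neither summary of changes mentions the SD.

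**The concern.** Required sample size grows with the square of the SD. Moving from 16.7 to 17.6 should raise it by a factor of (17.6/16.7)² = 1.11, about 11%, yet 312 and 390 do not move. At least one final document is therefore wrong, and a reader cannot tell which.

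Change in blood pressure is one of two co-primary outcomes. If 312 is too few for the stated effect, the advertised 80% power is not available once the plan's own 20% loss occurs. A null blood pressure result would then be read as coming from a trial with a 20% chance of missing a true 5 mmHg effect, when that chance is larger.

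**Working it through.** **Inputs.** Difference 5 mmHg; SD 16.7 (final protocol) or 17.6 (final analytic plan); power 80%; alpha 0.05; 1:1 allocation; 20% loss. A two-sided test is assumed.

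**Step 1. The inflation step reproduces.** 312 / (1 − 0.20) = 390. The fault is not here.

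**Step 2. Patients required.** n per arm = 2 (z₀.₉₇₅ + z₀.₈₀)² SD² / δ² = 2 (1.96 + 0.8416)² SD² / 25.

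| SD (mmHg) | n per arm | Evaluable total | Enrolled, ÷ 0.8 |
|---|---|---|---|
| 16.7 | 175.1 → 176 | 352 | 440 |
| 17.6 | 194.5 → 195 | 390 | 488 |
| Stated | 156 | 312 | 390 |

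The exact t calculation adds about two patients to each evaluable total (354 and 392).

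**Step 3. The SD that 312 implies.** SD = 5 × √(156/2) / (1.96 + 0.8416) = 15.76; about 15.7 on the exact t. Neither final document gives this value.

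**Step 4. Power with 156 per arm.** Standard error = SD × √(2/156); power = Φ(5/SE − 1.96).

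- SD 16.7: SE 1.891, 5/SE = 2.644, power 75.3% (exact t 75.1%).
- SD 17.6: SE 1.993, 5/SE = 2.509, power 70.9% (exact t 70.6%).

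The type II error is therefore about 25% or 29%.

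**Step 5. Difference detectable with 80% power at 312.** 2.8016 × SE = 5.3 mmHg (SD 16.7) or 5.6 mmHg (SD 17.6).

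**Step 6. If all 390 were observed.** Power is 84.1% (SD 16.7) or 80.1% (SD 17.6).

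**Step 7. Sidedness.** With z₀.₉₅ = 1.645 in place of 1.96, SD 17.6 needs 308 and SD 16.7 needs 276. The Morisky figure in the same paragraph is a cross-check: difference 0.5, SD 1.6, 195 per arm gives SE = 1.6 × √(2/195) = 0.162 and 0.5/SE = 3.086. Two-sided power is Φ(3.086 − 1.96) = 87.0%, which matches the stated 87%. One-sided power is Φ(3.086 − 1.645) = 92.5%, which does not.

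**Step 8. If the SD is that of a single reading.** The SD of the change is SD × √(2(1 − ρ)), where ρ is the correlation between the baseline and 12-week readings. The documents give no ρ. At ρ = 0.5 the totals stay at 352 and 390. At ρ = 0.6, SD 17.6 becomes 15.74 and gives 312, while SD 16.7 becomes 14.94 and gives 282.

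**The case against.** Four points can be made for the plan.

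1. **Sidedness is not written.** A one-sided 5% test at SD 17.6 needs 308, close to 312, and has 80.6% power at 312. This reading is not excluded by the text, but it is the weaker one. The null has no direction, and the Morisky 87% at the stated 390 is a two-sided figure. That cross-check is not conclusive alone, since one-sided power at 312 is also about 87%, but the text attaches the figure to 390. In any case SD 16.7 gives 276 one-sided, so the protocol's figure still fails.
2. **The meaning of the SD is open.** If 17.6 is the SD of a single reading and ρ is 0.6, the total is 312. That correlation would have to be supplied from outside the documents, and it gives 282 at SD 16.7. What stands is that the SD must be defined.
3. **The primary analysis is not restricted to completers.** Missing 12-week outcomes are multiply imputed using covariates and the week 4 and 8 readings; complete-case analysis is a sensitivity analysis. This stands as a qualification. Power could lie anywhere from 71% to 80% at SD 17.6, or 75% to 84% at SD 16.7, depending on what the earlier readings recover. Patients lost early may have none. The plan itself treats 312 as the number needed and claims no gain. Nor is a gain from baseline adjustment planned: covariates enter only if imbalanced, and baseline blood pressure is not listed.
4. **How the error arose is unknown.** At SD 17.6 the two-sided requirement is 390, and 312 is 0.8 × 390, so the allowance looks to have been taken off the required number instead of added to it. The two SDs are also digit transpositions of each other. Both are inferences, and the conclusion needs neither.

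**Conclusion.** The point holds. That the two final documents give different SDs for the same 312 and 390 is plain from the text. None of the readings tried, whether two-sided, one-sided or as a single-reading SD with a common correlation of 0.5 or 0.6, reproduces 312 in both.

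Under a two-sided 5% test, with the SD used as stated and nothing recovered by imputation, power for 5 mmHg at 312 evaluable is about 71–75%, not 80%. Keeping 80% after 20% loss would take 440 or 488 enrolled, against the 390 stated. The 71–75% is the lower end of a range whose upper end, with no information lost, is 80–84%. The shortfall is moderate, but it concerns a stated operating characteristic of a co-primary outcome and should be corrected before that power is relied on to interpret a null result.

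**What to change.** In the Sample Size sections of both the final protocol and the final analytic plan:

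- Use one SD, give its source, and say whether it is the SD of the change or of the 12-week value.
- State that the test is two-sided at 0.05.
- Replace the 80% claim with the figures the design delivers. Possible wording: *390 randomised, 312 evaluable after 20% loss: two-sided power for 5 mmHg is 71% at SD 17.6 (75% at SD 16.7), and 80% power is available for 5.6 mmHg (5.3 mmHg), assuming no information recovered by imputation.* Keep only the figures for the SD chosen.
- If a gain from imputation or baseline adjustment is to be claimed, state it beside these figures with the correlation assumed.

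The cost is a few sentences in two sections and a less favourable stated power. Enrolment, randomisation and analysis are unchanged.

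### The 87% power for the Morisky co-primary is computed on all 390 enrolled patients; at the plan's own 20% loss to follow-up it is about 79% (two-sided 0.05 assumed)

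*Supplement*

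**What the plan says.** The Sample Size section of the final analytic plan starts with blood pressure. It sets "a power of 80%, and an alpha of 0.05 there would" and continues: "need to be 312 patients enrolled. With allowance for 20% loss to follow-up, the study will seek to enroll" 390 in total. The allowance is consistent with itself, since 390 × 0.80 = 312.

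It then turns to adherence: "With a standard deviation of 1.6 (8) and a" "sample size of 390 patients, we will be able to detect a 0.5 Morisky score difference between the groups", "with a power of 87" per cent. The Sample Size section of the final protocol gives the same Morisky statement.

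Four other places bear on it:
- Final protocol, Outcomes: self-reported adherence is co-primary with the change in blood pressure.
- Final protocol, Study Procedures: the Morisky scale is collected at baseline and again in the 12-week exit questionnaire. Weeks 4 and 8 collect blood pressure only. Patients who miss the exit questionnaire or the final blood pressure reading are classed as lost to follow-up.
- Final analytic plan, Analytic Plan: missing 12-week outcomes are multiply imputed (5 imputations) from a list of demographic, clinical and phone-use covariates plus blood pressure at weeks 4 and 8. The list does not include baseline Morisky.
- Same section: the null "hypothesis will be that there is no difference in the change in blood pressure between the two groups after" 12 weeks. Neither document says whether tests are one- or two-sided.

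**The concern.** Within one paragraph, enrolment is inflated because a fifth of patients are expected to be lost, and then the power for a co-primary outcome is stated as if nobody were lost. The Morisky score has a single post-baseline measurement, and missing it is part of the plan's definition of loss, so nothing exempts this outcome from the 20%.

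At stake is how an adherence result is read. If it is null, a reader will take it that the trial had 87% power for half a point. If the figure under the plan's own assumptions is just under 80%, that reading is too confident, and the difference the trial could detect with 87% power is larger than the one stated.

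**Working it through.** **Inputs.** From the Sample Size section: difference 0.5, SD 1.6, alpha 0.05 (given for blood pressure and carried over, since no split is stated), 390 enrolled, 20% loss. From the final protocol: 1:1 allocation. Assumed: a two-sided test. The SD is taken as given.

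**Formula** (n per arm, normal approximation): power = Φ( 0.5 / (1.6 × √(2/n)) − 1.960 ).

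**1. Reproduce the plan's figure.** All 390 analysed, n = 195:
- 0.5 / (1.6 × √(2/195)) = 0.5 / 0.1620 = 3.086
- Φ(3.086 − 1.960) = Φ(1.126) = 0.870 (noncentral t: 0.868)

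This is the stated 87%, so the figure assumes a 12-week score from every enrolled patient.

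**2. Apply the plan's loss rate.** 390 × 0.80 = 312, n = 156:
- 0.5 / (1.6 × √(2/156)) = 0.5 / 0.1812 = 2.760
- Φ(2.760 − 1.960) = Φ(0.800) = 0.788 (noncentral t: 0.786)

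Power is about 79%, some 8 points below the stated figure. At half the planned loss (10%, 351 analysed) it would be 83%.

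**3. The same gap in other units.**
- Difference detectable with 87% power at 312: 1.6 × (1.960 + 1.126) × √(4/312) = 0.56 points, not 0.5.
- Patients needed for 87% at 0.5 points: about 392 evaluable, or 392 / 0.80 = 490 enrolled.

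**4. Multiple imputation.** Let R² be the share of the variance of the missing score that the imputation variables explain. The variance of the difference is approximately 1.6² × 2 × [ (1 − R²)/156 + R²/195 ], multiplied by 1 + 0.2(1 − R²)/5 for five imputations. The documents give no R², so the range is an assumption:

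| R² | Power, many imputations | Power, 5 imputations |
|---|---|---|
| 0 | 78.8% | 77.2% |
| 0.1 | 79.6% | 78.2% |
| 0.3 | 81.2% | 80.2% |
| 0.5 | 82.9% | 82.1% |

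In this formula 87% returns only at R² = 1, where the bracket becomes 1/195.

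**5. Baseline Morisky as a covariate** (312 evaluable). The standard error shrinks by √(1 − r²), where r is the correlation between baseline and 12-week scores (an assumption; the documents give none):
- r = 0.40: power 85.1% (noncentral t)
- r = 0.45: 2.760 / √(1 − 0.2025) = 3.091; Φ(3.091 − 1.960) = 87.1% (normal approximation)
- r = 0.50: power 88.8% (noncentral t)

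So 87% needs a correlation of about 0.45.

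**The case against.** The strongest defence is that sidedness is not stated. A one-sided 0.05 test on 312 patients gives 86.8%, which also rounds to 87%. With the analytic plan's blood pressure SD of 17.6, a one-sided test needs 308 patients, close to the stated 312. On that reading both outcomes rest on about 312 evaluable patients and the 87% already allows for loss. This has some force, and the plan should state sidedness. It does not rescue the sentence, which ties 87% to 390 patients; a one-sided test on 390 would give 92.5%. The stated null is one of no difference, and the two-sided figure at 390 matches.

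A second defence is that the primary analysis imputes missing outcomes and so keeps all 390. That is true, and it means 79% is strictly a complete-case figure. Imputation adds only what the predictors know about the missing score, though, and with no interim Morisky score among them that moves power by a few points at most over the range shown.

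Some stronger readings are tempting but not supported:
- A reader might infer that Morisky is more exposed to loss than blood pressure. The final blood pressure is requested at the same time point, missing either one counts as loss, and week 12 has an extra reminder email.
- A reader might infer that imputation recovers nothing. It can recover a little.
- A reader might infer that the two co-primaries truly rest on different numbers of patients. The wording suggests it, but the figures do not settle it: with SD 17.6 and a two-sided test, blood pressure itself needs 390 analysed. That is a separate question about the blood pressure calculation. The 312 used here is simply 80% of 390.
- A reader might add a penalty for splitting alpha between the co-primaries. The plan states no split, and multiplicity is a separate matter.

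**Conclusion.** The point holds. As written, the 87% applies only if all 390 enrolled patients supply a 12-week Morisky score, which conflicts with the 20% loss allowed for in the same paragraph. At 312 evaluable, power for a 0.5-point difference is about 79%, or roughly 77-82% for the imputed analysis over the assumed range of R².

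This rests on a two-sided 0.05 test (inferred from the null), SD 1.6 as given, and the plan's own loss rate; actual loss may differ.

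Severity is minor to moderate. A reader might infer that the trial is seriously underpowered for adherence or must enrol more. The documents do not support that: the corrected figure is about one point below the 80% the plan sets for blood pressure, the enrolment target is derived from blood pressure, and no estimate or test is invalidated.

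**What to change.** In the Sample Size sections of both the final protocol and the final analytic plan, replace the Morisky statement with: *with 312 evaluable of 390 enrolled and a two-sided alpha of 0.05, power is about 79% for a 0.5-point Morisky difference (SD 1.6)*. This costs one sentence in two places and leaves enrolment and analysis unchanged. It also supplies the missing statement of sidedness for this outcome. If a one-sided test was intended, the plan should say so and name the analysed number behind the 87%.

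Optionally, prespecify the baseline Morisky score, which is already collected, as a covariate in the adherence model. This is a change to the model rather than to a number, but it needs no extra patients or data. Any power quoted on that basis should give its assumed correlation: about 85-89% for 0.4-0.5.
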